Statistical Analysis Plan; Can Feedback from a Large Language Model Improve Health Care Quality?

[name]*, [name]† [name]‡ [name]§ [name]¶

April 29, 2025

1 Introduction

The quality of healthcare in low- and middle-income countries is notoriously low (Banerjee et al., 2023). In Nigeria, only a small proportion of primary care patients are seen by a Medical Officer instead of a mid-level provider such as a Community Health Extension Worker or Community Health Officer. Access to qualified medical doctors is a barrier to good health care (Okeke, 2023).

This project tests whether Large Language Models (LLMs) can improve patient care in Nigerian primary care clinics by giving customized and instant feedback to the provider in natural language. An LLM-based tool integrated into an electronic patient record management system provides “second opinions” to community health extension workers (CHEWs) at two clinics in Nigeria. These second opinions are intended to mirror what a reviewing physician might advise the CHEWs after seeing or hearing their initial report on a patient.

2 Experimental Design

For our main analysis, we use a within-patient comparison of two patient notes created by the CHEW; one during the initial patient consultation, and one after the LLM feedback was received. The patient is also seen by a fully trained medical officer who is in charge of patient care. The MO conducts a blinded review of the CHEW’s patient notes to measures changes in the CHEW’s care as a result of the LLM feedback. Our data comes from the information captured in the electronic medical record (EMR) of the patient and from survey data collected from CHEWs, reviewing MOs, and a panel of reviewing Medical Doctors (see below).

As part of the research protocol, we also conduct screening tests for malaria, anemia, and UTI (urine analysis). Eligibility for each test is determined using a set of symptoms explicitly checked by the enumerator, and patient demographics (see Appendix A). Tests that were already ordered by the MO and carried out are not repeated (based on EMR information). The criteria were designed as broad as possible, with the goal to test any patient who should be tested or would be recommended for testing in typical clinic practice by at least some providers. Note that CHEWs as part of this study are not able to order any medical tests for ethical reasons. In daily practice, they have a limited set of tests available, primarily rapid diagnostic tests (MOs can order all medical tests that CHEWs can order plus others).

2.1 Sample size

We work with a private clinic and the project is grant funded. The clinic manages the budget directly and projects that funds are sufficient to collect valid data from approximately 500 patients. The intervention is carried out by 20 CHEWs who are rotating through two clinics. Data collection will be conducted until the grant budget is exhausted.

*Yale School of Management, Yale University

†Department of Computer Science, George Washington University

‡EHA Clinics Nigeria

§Development Research Group, The World Bank, [name]

¶Department of Medical Ethics and Health Policy and Department of Medicine, University of Pennsylvania School of Medicine

2.2 Patient EMR data

All patient data is saved in the EMR. At various points, this data is collated into SOAP notes (structured text files describing subjective and objective signs and symptoms, the provider's assessment (diagnosis), and the treatment plan).

The SOAP notes that are saved are:

- “Unassisted” SOAP note created on initial patient consultation and submitted to LLM: contains care plan conditional on results of requested medical tests, randomly labeled SOAP A or B
- “Assisted” SOAP note created after LLM feedback was received: conditional care plan, randomly labeled B or A
- Conditional MO SOAP note: conditional care plan, created by MO prior to receiving laboratory test results
- Patient discharge SOAP note: patient care plan created by MO after receiving laboratory test results and communicated to patient
- Final MO SOAP note: patient care plan created after reviewing study medical tests (malaria, anemia, UTI).

In addition, we have the values of individual EMR fields that make up these SOAP notes, e.g. test results, diagnoses, prescriptions, etc., including patient demographics and vital signs.

2.3 Survey Data

We collect various forms of survey data; the key information about the quality of care provided by the CHEW (either without or with LLM assistance) comes from the MO's evaluation of the CHEW's SOAP notes for every patient. We also collect CHEW feedback on the LLM's advice, for each patient and overall; and a survey for a panel of MDs who conduct a second evaluation of the CHEW notes, review the LLM feedback, and assess the MO's care plan.

2.3.1 The MO's SOAP note evaluation

The evaluation focuses on treatment errors in the SOAP note that could cause some form of (medical) harm to the patient.

For each SOAP note, the MO first takes stock of qualitative differences between the CHEW's and the MO's plan, then assesses the type of harms for the patient from any errors, and finally rates the SOAP note on a scale for “healthy time lost”. The MO is blinded to whether the SOAP note is LLM-assisted or unassisted and rates SOAP Note A before seeing SOAP Note B.

Deviations from the MO's SOAP The MO is asked to assess for each SOAP note whether medical tests ordered were necessary or clinically useful vs. unlikely to be useful, whether there are missing or incorrect/unnecessary diagnoses, and whether there are missing or incorrect/unnecessary treatment plan elements.

Types of harm incurred The MO is asked to assess any short-term harm (additional symptoms or discomfort for some period), and any long-term serious harm (risk of impairment, death etc.) from the treatment plan in the SOAP note.

Measuring Healthy Time Lost in DALY The MO also provides an overall rating that is intended to reflect the “healthy time lost” from any errors in treatment in the SOAP note. For each assessment and plan constructed by a CHEW (with or without LLM advice), an MO will assess the expected magnitude of healthy life that would be lost if the CHEW plan were implemented instead of the MO's plan. Healthy time is measured in units of disability-adjusted life year (DALYs), which reflect both length and quality of life. Losing one DALY is equivalent to losing a year of life in perfect health, or two years of life experienced in an unhealthy state with a utility weight of 0.5, etc.

MOs estimate DALY losses with the aid of a DALY scale. The DALY scale consists of a set of cutoff points that were calibrated using benchmarks of expected DALY loss for clinical mistakes relevant to local medical practice. Because the DALY consequences of permanent harm (death or disability) are higher for children than for adults, and because different clinical mistakes are relevant for children and adults, we provide a separate DALY scale for the evaluation of CHEW notes for patients who are children (under 18) and patients who are adults.

DALY benchmarks are derived from previously published DALY or QALY estimates from the medical research literature, and from novel calculations of expected harms, which employ prior estimates of the utility weights of various health states, of the effects of various medical interventions, and of life expectancy in Nigeria (both absolute and quality adjusted).

To create a consistent scale, specific DALY benchmarks are associated with cutoff points that are described in broad clinical terms, capturing the general nature of the harms.

MOs will first be presented with the following survey prompt:

“Consider the overall health harms from the treatment errors in SOAP Note [A/B] that you just described (temporary symptoms and risk of longterm or permanent harm).

The scale below shows levels of harm that average [adults/children] experience due to different medical errors, ordered from least to most severe.

Harm is expressed in terms of ‘healthy time lost’.

For example, unpleasant symptoms for 6 days reduce quality of life by 1/3 for those days, resulting in the equivalent of 2 days of life lost.

Please select the appropriate interval of the harm scale for SOAP Note [A/B].”

Below this prompt, the scale of different levels of harm is shown in table form, as in figure 1.

[figure not shown]

Figure 1: Initial Rank Ordering (Adult Scale)

The MO uses the multiple-choice response option in the bottom to select an interval on the scale.

On the next screen, they see a detailed description of the two scale end-points and use a slider to choose the estimated level of harm between those two points, see Figure 2 for an example.

The DALY scale has 9 benchmarks from 0 minutes to 23 years (28 years for children), generating 8 “bins” each. They are described in detail in Appendix C.

2.4 CHEW Feedback

After completing the evaluation of each patient, CHEWs choose on a scale from strongly disagree to strongly agree for three statements:

“In my opinion, the LLM feedback helped me improve the documentation of the patient’s case.”

“In my opinion, the LLM feedback helped me provide better healthcare for the patient.”

[figure not shown]

Figure 2: Example of Healthy Time Loss Quantification

Like avoiding an unnecessary test, prompting me to provide better advice to the patient, or prompting me to choose a better medication”

“In my opinion, the LLM feedback contained a medical error.”

(If yes: "Please briefly describe the error.")

In addition, CHEWs respond to a more general feedback questionnaire when they rotate out of the study.

2.5 MD Panel

A panel of three Medical Doctors (MDs) will review the patient data (CHEW notes, MO notes, and LLM feedback).

Flagging MO error. In a first step, they will review the MO notes only and record whether there is any error in the diagnosis or treatment proposed in the conditional note or in the final note. If an error is identified the MDs will rate the error by severity to distinguish medical mistakes from differences in opinion about a patient who is not present.

SOAP note rating. Next, the MDs will carry out an independent evaluation of the assisted and unassisted SOAP notes as described in the sections “Types of harm incurred” and ”“Measuring Healthy Time Lost” (section 2.3.1 above).

LLM review. Finally, the MDs will also review the LLM feedback and answer the following questions:

“Did the CHEW follow all, some, or none of the LLM recommendations?”

If some or none: "Imagine the CHEW had followed all the recommendations of the LLM. Would the resulting treatment plan be an improvement over their assisted note?" (Yes/no)

If yes: "Please explain."

“Did the LLM make any mistakes?” (Yes/no)

If yes: "Was any aspect of the CHEW's assisted treatment plan worse than the unassisted plan because the CHEW followed the LLM's erroneous recommendation?"

If yes: "Please explain."

3 Primary Outcomes

Our study will have four primary outcomes, each assessing differences between the CHEW's assisted and unassisted note.

1. An indicator for an error in the treatment plan in the SOAP note (with the potential for harm)
2. An indicator for an error in the treatment plan that causes a loss of at least X quality-adjusted life days (where X is the highest benchmark on the appropriate DALY scale so that at least 5% of patients have an error that large in the unassisted SOAP note)
3. An indicator for the better treatment plan

4. Consistency of treatment with the “standard of care” based on our screening tests and medical guidelines.

We describe the construction of each metric in detail below.

3.1 Estimation

The primary analysis estimates the effect of LLM assistance on the four outcomes above, all broad indicators for the overall quality of care provided. Every outcome is measured both for assisted and unassisted SOAP notes. We will estimate

$$Y_{it} = a_i + bT_k + cX_{ik} + \epsilon_{ik}$$

where i is the patient (or patient-test combo in 3.5) and $k = \{A, B\}$ is the SOAP note. Y_{ik} is the outcome, a_i is a patient (patient-test) fixed effect, T_k is an indicator for “assisted” and X_{ik} are optional controls for order effects and unblinding (see next section).

We will calculate robust standard errors. In addition, we will separately report p-values using the Benjamini Hochberg procedure for controlling false discovery rates at $p = 0.05$. This will lead to a conservative estimate of the power of our statistical tests. We will also separately report means, standard deviation, and number of observations of each variable for the assisted and unassisted notes.

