5.1 Blinding

We will conduct checks to control for the possibility that imperfect blinding to the intervention (i.e. MO knowledge whether a patient note was “LLM assisted” or not) is impacting our results.

- We measure each MO’s beliefs about whether a given patient note was LLM-assisted with a survey question. We will analyze whether MO beliefs about whether a note was LLM assisted are predicted by true LLM assistance status.
- As a robustness check, we will control for MO beliefs about LLM assistance and for any order effects (i.e. identity of note A vs. B) in the main analysis.
- Ex post, if we find that MOs can reliably predict whether a note was LLM assisted, we will seek to identify whether there are specific outcome-irrelevant features of notes which aid in this prediction, and may run additional robustness checks on a subset of patients where this feature was absent, so blinding is better maintained.

Bias in the difference in evaluation between notes A and B can arise if the MO (i) correctly guesses which note is assisted by the LLM, and (ii) systematically rates notes more highly if they are assisted by the LLM, but *not* due to higher quality of care/true lower harm to the patient.

For the first note that each MO sees (note A), we elicit a “raw” evaluation score prior to seeing note B. This score is then amended into an “adjusted” final evaluation (the reason for the update is the potential for learning about note A, given the cognitively demanding task of the MO: for example, only when shown the highlighted differences between the two notes may the MO detect an error in note A.) In an ideal world, the “adjusted” rating simply reflects the MO’s evaluation given full information. This is the measure we use in most of our analysis. However, the “raw” score provides an opportunity for another blinding check, under the assumption that blinding is more problematic for note B than note A.

If this is the case, a cleaner but noisier estimate of our main effect can be obtained by using an across-patient comparison of the “raw” scores of assisted and unassisted SOAP notes A. This regression will be identical to our baseline specification, but omitting the patient fixed effects.

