5.4 Updates 4/29/2025

We have several updates to the pre-analysis plan – these updates are made prior to analyzing the data by treatment status.

On 2/25, we discovered a randomization error in the order of the notes as presented to the MO (the unassisted note was always presented first, rather than in random order). Due to this error, we are throwing out all observations from prior to 2/25 in any analyses that use MO generated outcomes. Analyses that rely on outcomes not generated by the MO (e.g. objective test data) will still use all data, including the data gathered prior to 2/25.

As a result of these changes, we are extending the timeline of the initial study. The current proposed end date is May 30th.

A Criteria for Screening Tests

We apply the following demographic and symptom screening criteria for the medical screening tests.

Malaria RDT: All demographics are eligible. Malaria testing is offered if the patient reports a fever in the last 24 hours.

Anemia/PCV: All patients 18 years and older.

The test is offered for patients reporting feeling tired or with low energy for 4 weeks or more, feeling like their heart is racing for 4 weeks or more, signs of bleeding for 4 weeks or more (vaginal bleeding, blood in stool or in urine), feeling dizzy, difficulty breathing, currently pregnant, and delivered a baby within the past six weeks.

Urine dipstick analysis: Only female patients 7 years or older.

Urine dipstick analysis is offered for patients reporting pain while urinating, blood in urine, frequent urge to urinate, abnormal discharge from the genital area, and burning feeling while urinating.

B Treatment guidelines for malaria, anemia and UTI

- For malaria, conditional on testing positive (and meeting the symptom screen), the essential treatment guidelines are:

Adults: Artemether-Lumefantrine 80 mg/480 mg by mouth twice daily for 3 days

Children 5-14 Kg: Artemether-Lumefantrine 20 mg/120 mg by mouth twice daily for 3 days

Children 15-24 Kg: Artemether-Lumefantrine 40 mg/240 mg by mouth twice daily for 3 days

Children 25-34 Kg: Artemether-Lumefantrine 60 mg/360 mg by mouth twice daily for 3 days

Severe malaria: Artemether 3.2 mg/Kg IM loading dose once followed by 1.6 mg/kg IM maintenance dose once daily for 3 days

- For anemia, conditional on testing positive (and meeting the symptom screen), the essential treatment guidelines are:

Adults: Ferrous Sulfate 200 mg by mouth once daily for one month

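### For the three MO-rated primary outcomes, the randomised A/B position should be a fixed term in the primary model; as an optional control it leaves the headline specification implied and may lose a little precision.

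*SAP*

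**What the plan says.** Section 2.2 states that the unassisted note is "randomly labeled SOAP A or B" and that the assisted note takes the other letter. Under section 2.3.1 the MO "rates SOAP Note A before seeing SOAP Note B". Section 3.1 then gives one estimating equation for all four primary outcomes. In it, "a_i is a patient (patient-test) fixed effect, T_k is an indicator for “assisted". The remaining term, X_ik, is described as "optional controls for order effects and unblinding", with a pointer to the section after it.

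The section that follows, 3.2, defines the any-error outcome and does not mention these controls. Section 4, if that is the section meant, does not mention them either. They appear in 5.1: "As a robustness check, we will control for MO beliefs about LLM assistance and for any order effects (i.e. identity of note A vs. B"). The same sentence places this control within the main analysis.

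Section 5.4 reports that before 2/25 "the unassisted note was always presented first, rather than in random order". For that reason it drops the earlier data from analyses of MO-generated outcomes and keeps them for the other outcomes.

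**The concern.** Position is randomised, always known and fixed before rating. The review flow also treats the two positions differently. Note A gets a raw score that is later adjusted (5.1), and Note B is reviewed only if the MO answers yes or unsure on whether the plans differ meaningfully (3.4). An order effect is therefore possible. Because position varies within patient, the fixed effect does not remove it, and without a position term it stays in the residual.

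The wording also joins two unlike variables. Position is set by chance. MO belief about assistance is recorded after the intervention and can be affected by what the LLM changed in the note, so adjusting for it may remove part of the effect. As written, X_ik could hold neither variable, position only, belief only or both. At stake are some precision in a sample whose size is set by budget, and a clear statement of which model gives the headline result.

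**Working it through.** The SAP states no power or precision figure to reproduce. Section 2.1 gives only a budget projection: "funds are sufficient to collect valid data from approximately 500 patients".

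**Reduction to a difference.** With two notes per patient, the fixed-effect model is the same as a model for the within-patient difference (assisted minus unassisted):

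D_i = b + g·P_i + e_i

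P_i is +1 if the assisted note is B and -1 if it is A, each with probability 1/2. The assistance effect is b, the B-versus-A position effect is g, and s² is the variance of e_i.

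- Without position: Var(b̂) = (g² + s²)/n
- With position: Var(b̂) ≈ s²/n
- Share of variance saved: g²/Var(D). For a binary outcome Var(D) = d - b², where d is the share of patients whose two notes differ on the outcome.

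**Assumed inputs** (none is in the SAP except n): n = 500, d = 0.30, b = -0.05, two-sided 0.05, one outcome without the Benjamini-Hochberg step. Then Var(D) = 0.30 - 0.0025 = 0.2975, and the SE without position is √(0.2975/500) = 0.0244.

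| Order effect g | Variance saved, g²/0.2975 | SE without → with | Power without → with | Equivalent extra patients |
|---|---|---|---|---|
| 0 | 0% | 0.0244 → 0.0244 | 53.6% → 53.6% | 0 |
| 0.05 | 0.8% | 0.0244 → 0.0243 | 53.6% → 53.9% | 4 |
| 0.10 | 3.4% | 0.0244 → 0.0240 | 53.6% → 55.0% | 17 |
| 0.20 | 13.4% | 0.0244 → 0.0227 | 53.6% → 59.6% | 78 |

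**Range.** The share saved does not depend on n. Over d = 0.2 to 0.5 it is about 0.5-1.3% at 5 points and 2-5% at 10 points. At 20 points it is 8-14% for d = 0.3 to 0.5.

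**Severe error (outcome 2).** Section 3.3 sets the cut-off at the 95th percentile of unassisted harm. If about 5% of notes of each kind qualify, d is at most about 0.05 + 0.05 = 0.10, so the SD of D is at most about √0.10 = 0.32. An order effect of 10 points or more is not credible for so rare an event. One of 2 points would save 0.0004/0.10 = 0.4% at that upper limit of d.

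**Chance imbalance.** The mean of P_i has SD 1/√500 = 0.045. With g = 0.10 this moves the estimate by an SD of 0.0045. Its square is g²/n = 0.00002, which is exactly the variance term already counted above and not a further loss.

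**Bias and type I error.** In simulation with robust SEs (n = 500, d = 0.30), both models centred on the true effect. With no true effect, each rejected in about 5% of runs. Reporting whichever of the two was significant rejected in 5.2%, 5.6%, 6.0% and 6.8% of 40,000 runs at order effects of 0, 5, 10 and 20 points. The Monte Carlo SE is √(0.05·0.95/40000), about 0.1 point. Models that also adjust for belief were not simulated.

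**The case against.** The strongest defence is that nothing is invalid. Under random labelling the unadjusted estimate is unbiased and holds its level, and an unadjusted primary analysis with an adjusted check is a legitimate choice. Section 5.1 commits to the adjusted check, so the choice is neither hidden nor wide open. The design also limits order effects: most analyses use the adjusted Note A score, and when no meaningful difference is declared, outcome 3 is 0 for both notes whatever their position. All of this stands, and it limits the point to a clarification with a modest gain.

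Three stronger readings are tempting, and the SAP supports none of them.

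- A reader might infer that omitting position biases the effect. It does not where labels are random, and the MO-rated analyses keep only data from 2/25 onward.
- A reader might take the discarding of earlier MO ratings as the sponsor's own evidence of a large order effect. In those data position was fully confounded with assistance, so no covariate could have separated the two. The exclusion says nothing about the size of an order effect once order is random.
- A reader might infer free choice among many specifications. Read together, 3.1 and 5.1 point to the unadjusted model as the headline, and choosing between the two models would raise type I error only to about 5-7%.

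The defence does not answer two things. No sentence names the headline model, and position and belief share one optional term although they need different treatment.

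**Conclusion.** The point holds as a minor but worthwhile clarification for outcomes 1-3. The primary specification is implied rather than stated, and a covariate that the trial itself randomises is left out of it by default.

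The precision at issue is nil with no order effect and up to about 5% of the variance at 10 points. It reaches 13-14% only at 20 points with 30% discordance (0.04/0.2975 for a 5-point assistance effect, 0.04/0.29 for a 10-point one). For severe error it is likely to be negligible. Every one of these figures rests on assumed discordance and order effects, since the SAP gives neither. Validity is not threatened.

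Outcome 4 is outside the point. It rests on test results and note content rather than on the order in which the MO read the notes, and it keeps pre-2/25 data in which position and assistance coincide.

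**What to change.** For outcomes 1-3, on data from 2/25 onward, state one primary model:

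Y_ik = a_i + b·Assisted_ik + c·PositionB_ik + e_ik

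- Delete the word optional from 3.1.
- Report the model with MO belief added as a sensitivity analysis only.
- Point the cross-reference in 3.1 to section 5.1.
- State that outcome 4 is estimated without the position term, and why.

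The cost is a few lines of text and one degree of freedom, with no new data. The change should be dated before any analysis by treatment status, as section 5.4 says of its own updates.

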3.5 Treatment Misallocation Based on Objective Conditions

All at-risk patients in our study will receive malaria, anemia and UTI screening. We define eligibility for testing in Appendix A and the treatment guidelines for each condition in Appendix B.

We will construct a dataset with one observation for each (patient, screening test, note), up to six per patient. We exclude (patient, test) data pairs where the test was not conducted due to our demographic criteria (only women/girls 7 years of age or older are tested for UTI, only adults are tested for anemia). We include (patient,test) combinations where our symptom screen determines the patient is eligible but does not need to be tested and label them as zeros.

We construct an indicator of treatment misallocation that records whether a patient was incorrectly treated for a condition based on the test result or lack of symptoms. The variable is coded as 1 if the patient tested positive and either received inappropriate or no treatment according to the guidelines above. It is also coded as 1 if the patient tested negative or was not tested based on the symptom screen but received treatment for the condition. The variable is only coded as zero if the patient tested negative and was correctly not treated for the corresponding condition, or if they tested positive and received the correct treatment.

Note that some treatments can be given for other conditions or without a screening test, such as antibiotics or iron supplements. In cases where the test was negative but a relevant treatment was received, an MD will conduct a blinded review and code the observation as either a match or mismatch. We will use the “clinical indication,” a diagnosis code that is recorded for each individual prescription drug, as auxiliary data for this exercise.

In cases where the provider created a treatment plan that conditions on the result of medical testing we will interpret this plan based on the actual test results. For example, if the CHEW recommends a malaria test and the plan contains the correct malaria treatment conditional on a positive test result and no malaria treatment when the test is negative, the indicator will equal 0 for both a positive and a negative test result.

4 Secondary Outcomes

Our study will also estimate effects on a range of secondary outcomes. Unless otherwise indicated we will use the same analysis approach as above.

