4.2 Objective Misallocation of Treatment – Alternative Specifications

As auxiliary outcomes, we will run the same treatment misallocation regression as in Section 3.5 separately for each possible test (with only patient fixed effects).

In addition, we will assess the contribution of different types of non-compliance with test results by coding patient-test-note level indicators for

- Misallocation due to overprescription: a condition is treated that the patient is confirmed not to have
- Misallocation due to undertreatment: a condition the patient is confirmed to have is not treated
- Misallocation due to incorrect dosing or drug choice: a condition the patient has is treated but the dosing or medication chosen is inappropriate.

Note that the misallocation indicator in Section 3.5 is the union of all three of these cases. We will test each of these three as dependent variables in the same regression as the misallocation indicator.

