4.4 Medical Testing Decisions

We will assess the potential misallocation of medical testing in two ways. First, we will measure it based on the screening test outcome. For each test type, we will create an indicator that is coded as 1 if the CHEW recommends conducting a test that turns out to be negative, and a second indicator that is 1 if the CHEW neglects to request a test that turns out to be positive.

Second, we will also construct a (patient,test,note) level indicator that measures whether the CHEW and MO requested the same or a comparable medical test (e.g. the CHEW requested a malaria RDT whereas the MO requested a malaria bloodsmear).

Finally, we will combine these indicators and count as a mismatch if and only if either: i) a test was not requested by the CHEW but was positive, or ii) the test was requested by the cCHEW but the result was negative and no equivalent test was ordered by the MO. This accounts for the possibility that good clinicians might sometimes order tests which are more likely to be negative “just in case”.

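### Primary outcome 4 counts up to three note comparisons per patient, but the SAP names no clustering by patient

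*SAP*

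**What the plan says.** Section 3.1 gives one regression for all four primary outcomes. Its index is defined as "where i is the patient (or patient-test combo in 3.5"), with a fixed effect at the same level. The only statement on variance estimation is "We will calculate robust standard errors". No section names a cluster level.

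Section 3.5 sets up outcome 4: "We will construct a dataset with one observation for each (patient, screening test, note), up to six per patient". Demographic limits reduce the count for some patients: "only women/girls 7 years of age or older are tested for UTI, only adults are tested for anemia". Pairs that pass these limits but are not tested because of the symptom screen stay in the dataset.

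The opening of section 4 carries the method over to secondary outcomes: "Unless otherwise indicated we will use the same analysis approach as above". Section 4.2 splits misallocation into three components and says "We will test each of these three as dependent variables in the same regression as the misallocation indicator". It also repeats the analysis "separately for each possible test (with only patient fixed effects"). In section 4.4, "we will also construct a (patient,test,note) level indicator that measures whether the CHEW and MO requested the same or a comparable medical test".

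**The concern.** A patient-test fixed effect removes the level of each pair. It does not remove correlation between the differences of one patient. Those differences share the same CHEW, the same two notes and one LLM message. A CHEW who revises broadly after feedback, or ignores it, can move the malaria, anemia and UTI results together. If the differences are positively correlated, the pooled regression treats them as more independent information than they are, and the standard error comes out too small.

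Reading robust as cluster-robust on the model's own unit does not help, because for outcome 4 that unit is the patient-test pair.

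At stake is the p-value of one of four primary outcomes, and the one built on objective test results rather than MO ratings. It then enters Benjamini-Hochberg, which takes its inputs as valid. The three pooled components in 4.2 inherit the problem, as does the patient-test-note indicator in 4.4 when tests are pooled.

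**Working it through.** The SAP states no standard error, power or correlation, so there is no figure of its own to reproduce beyond the row count: 3 tests × 2 notes = 6 rows, that is 3 paired differences.

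**Inputs from the SAP.** Differences per patient (3.5, Appendix A): adult women 3; adult men and girls aged 7–17, 2; other children 1. About 500 patients and 20 CHEWs (2.1). Level 0.05 (3.1), taken as two-sided.

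**Assumed.** Correlation ρ between a patient's differences, and the patient mix.

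**Formula.** Without the optional controls, the estimate of b is the mean of the pair differences. With k differences per patient, DEFF = 1 + (k−1)ρ. In a mixed sample, DEFF = 1 + ρ·Σk(k−1)/Σk. True over reported SE = √DEFF. Type I error = 2[1 − Φ(1.96/√DEFF)].

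**Same number of tests for every patient**

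| ρ | SE ratio, k=2 | Type I, k=2 | SE ratio, k=3 | Type I, k=3 |
|---|---|---|---|---|
| −0.1 | 0.949 | 3.9% | 0.894 | 2.8% |
| 0 | 1.000 | 5.0% | 1.000 | 5.0% |
| 0.1 | 1.049 | 6.2% | 1.095 | 7.4% |
| 0.2 | 1.095 | 7.4% | 1.183 | 9.8% |
| 0.3 | 1.140 | 8.6% | 1.265 | 12.1% |

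**Mixed samples** (percent of patients with three/two/one tests)

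| Mix | Σk(k−1)/Σk | Type I, ρ = 0.1 | Type I, ρ = 0.3 |
|---|---|---|---|
| 30/40/30 | 2.6/2.0 = 1.300 | 6.5% | 9.6% |
| 50/30/20 | 3.6/2.3 = 1.565 | 6.8% | 10.6% |
| 60/20/20 | 4.0/2.4 = 1.667 | 7.0% | 11.0% |

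**Simulation under no effect** (500 patients, 50/30/20 mix, 20% discordant pairs, 6000 runs)

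| Realised ρ | Unclustered | Clustered by patient |
|---|---|---|
| 0.00 | 4.8% | 4.7% |
| 0.12 | 7.2% | 5.1% |
| 0.22 | 9.2% | 5.0% |
| 0.32 | 10.6% | 4.9% |

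**Which cluster level.** A separate simulation (500 patients, all with three tests, ρ about 0.32, 4000 runs) gave rejection rates of 13.2% with HC1 errors, 13.2% clustering on the patient-test pair, and 4.8% clustering by patient. The average SEs were 0.0115, 0.0115 and 0.0147, against a true SD of 0.0148.

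**Degrees of freedom.** In the same simulations at ρ = 0, robust errors without a correction for the absorbed fixed effects rejected about 16% of the time. With the usual correction the rate was about 5%. This is a further reason to name the estimator.

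**CHEW level**, relevant only if inference is meant to reach beyond these 20 CHEWs. With 500/20 = 25 patients each, ICC = SD²/discordance and DEFF = 1 + 24·ICC.
- 30% discordant pairs (assumed), between-CHEW effect SD of 5 points: ICC = 0.05²/0.30 = 0.0083, DEFF 1.20, type I error 7.4% by formula and 7.3% by simulation.
- The same with SD of 10 points: ICC 0.0333, DEFF 1.80, 14.4% by formula and 15.0% by simulation.
- A rarer outcome such as outcome 2 (assumed 8% discordant, SD 2 points): ICC 0.005, DEFF 1.12, 6.4% by formula and 6.5% by simulation.
- A CHEW-level t test on 19 df stays at 5.1–5.3% in the 30% discordant scenarios.

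**The case against.** The strongest reply is that ρ may be small. Appendix A triggers the three tests by largely different symptoms. Pairs kept without a test become misallocations only if the condition was treated anyway, so many differences will be exactly zero. If a share q of pairs can change at all, independently across tests, and changes among those pairs correlate at r, then ρ is about q·r. With 0.3 for each (assumed), ρ = 0.09, and the 50/30/20 mix gives 6.7%. At ρ = 0.05 it gives 5.9%, and at 0.02 it gives 5.4%. This stands: a modest excess is as consistent with the SAP as the larger figures. Uneven discordance also tempers the effect. With one test at 30% discordance and the others at 5% each, simulated error was 7.0–8.1% unclustered and 4.8–4.9% clustered by patient.

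The column for three tests would require every patient to be an adult woman, so it is an upper bound and the mixed samples are the better guide. That also stands.

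The CHEW figures concern a different inferential target, and the SAP describes a within-patient comparison. They do not support the main point and are given only for a sensitivity analysis. Section 4.4 does not say outright that tests are pooled; that part applies if they are.

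The per-test regressions in 4.2 have one pair per patient and are unaffected, so a reader can look at each test without stacking. They are auxiliary, however, and do not replace the pooled primary p-value.

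None of this removes the gap. The text names no level, and its own unit is the wrong one to cluster on.

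**Conclusion.** The concern holds. As written, the plan for outcome 4 ignores correlation between a patient's differences. If that correlation is positive, the reported standard error is too small and the type I error exceeds 5%: about 6.5–11% for correlations of 0.1–0.3 in the mixed samples, and less below 0.1. If it is zero there is no harm, and if it is negative the planned test is conservative. The SAP does not settle which case applies, and both the correlations and the patient mixes are assumptions. Clustering by patient is valid whatever the sign, for inference conditional on these 20 CHEWs and with about 500 clusters.

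Outcomes 1–3 and the per-test regressions in 4.2 are not affected at patient level, provided the usual degrees-of-freedom correction is made. The omission is certain and its effect uncertain but plausibly moderate. It touches a primary p-value and should be fixed.

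**What to change.** State in section 3.1 that standard errors are clustered by patient in every regression, including the stacked outcome 4 and the pooled patient-test-note analyses in 4.2 and 4.4, and that these p-values enter Benjamini-Hochberg. Add, as a sensitivity analysis, CHEW-clustered inference with a method suited to few clusters (wild cluster bootstrap-t, or CR2 with Satterthwaite degrees of freedom). Make that the main analysis only if the sponsor states that inference is meant to reach beyond these 20 CHEWs.

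The cost is one or two sentences and a code option, with a patient and a CHEW identifier on each note. Intervals will be somewhat wider if the differences are positively correlated. Fixing the level before data are analysed by treatment status also removes an analyst's choice.
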